## **8 INTERVENTION DISCONTINUATION**

Participation in this study is voluntary. If a participant discontinues the intervention, the participation in the follow-up of outcomes will be encouraged. If the participant is unable to come to any visits due to a conflict in their schedule, we will accommodate and try to complete their visit earlier or later to maximize the participation.

## **9 STATISTICAL CONSIDERATIONS**

### **9.1 General Design Issues**

This is an individual level, randomized, parallel-arm trial testing the primary hypothesis that a low sodium meal plan will reduced seated systolic blood pressure after about 14-days of feeding, compared to a typical sodium meal plan. For additional details please refer to our statistical analysis plan.

### **9.2 Sample Size and Randomization**

To detect the difference in seated SBP observed in the DASH-Sodium trial at 2-weeks (-9.53 mm Hg, standard deviation of 10.46, a type 1 error of 0.05 with 80% power), we would need 20 people in both arms (total 40). We will recruit 45 participants to account for a 10% attrition rate. Effect and variance data from the other endpoints will be used for sample size calculations in subsequent proposals.

#### **9.2.1 Treatment Assignment Procedures**

Participants will be randomized using a computer-generated randomization scheme with varying sized blocks to 1 of 2 sequences in a 1:1 ratio such that approximately half of participants will undergo the low sodium diet intervention, while the other half will undergo the usual sodium meal

plan intervention. Sex will be used as a stratification variable to ensure that sex is evenly distributed between interventions.

### **9.3 Interim analyses and Stopping Rules**

Not applicable: Given the short duration of the study, no interim analyses have been planned.

### **9.4 Outcomes**

#### **9.4.1 Primary outcome**

Seated systolic blood pressure measured during the follow-up visit.

#### **9.4.2 Secondary outcomes**

- a. Seated diastolic blood pressure
- b. Standing blood pressure
- c. Orthostatic hypotension
- d. Timed Up and Go Test
- e. Urinary sodium, potassium, and creatinine excretion
- f. Orthostatic symptoms

### **9.5 Data Analyses**

#### **Primary analysis**

We will first confirm that the residuals of seated blood pressure are normally distributed (if not then it will be log-transformed). We will compare net effect of reduced sodium versus usual diet on 2-week seated blood pressure. This comparison will be performed by fitting a linear regression with adjustment for baseline seated blood pressure. We will perform an intent-to-treat analysis.

Our hypothesis is that 2-weeks of low sodium dietary intervention will lower seated blood pressure compared to 2-weeks of usual sodium diet. The null hypothesis is that there will be no difference in seated blood pressure between the two intervention arms. The comparison between the two treatment groups will be performed by comparing the regression coefficient for treatment with zero (two-sided Wald test at 0.05 significance level).

#### **Secondary Pre-specified Subpopulations Analysis**

We will repeat the primary analysis to compare subpopulations based on the following criteria:

1. Baseline antihypertensive use (yes vs no)
2. Baseline diabetes (yes vs no)
3. Sex (men or women)

We will fit general linear models including a subpopulation of interest as a main effect term and an interaction with treatment term. The interaction terms will be used to assess for effect modification by baseline characteristic. Note these analyses are contingent on having sufficient number of participants with and without baseline antihypertensive use. Other stratified or subpopulations analyses based on baseline characteristics may be performed for hypothesis generation beyond the main study.

### Sensitivity analyses

1. Models from the analyses specified above will be fit with and without adjustment for baseline seated blood pressure.
2. We will perform three separate on-treatment analysis: (i) participants who ate 25% or less of non-study foods during the low sodium intervention, (ii) participants whose estimated calorie intake was met or exceeded by the food provided through the low sodium intervention, and (iii) persons who did not change antihypertensive medications during the post-randomization study period

### Analyses of other outcomes

- **Compliance:** Compliance will be quantified by (i) counts and proportion of participants who ate 25% or less of non-study foods during the low sodium intervention, (ii) counts and proportion of participants whose estimated calorie intake was met or exceeded by the food provided through the low sodium intervention. The data will be reported by treatment group and overall.
- **Secondary Endpoints:** We will examine the effect of the low sodium diet on the following additional outcomes, testing the null hypothesis that there is no difference in the following outcomes between the low sodium diet and usual sodium diet intervention. Continuous outcomes will be evaluated using linear regression to compare change between the 2 interventions arms with and without adjustment for baseline. We will examine the distribution of all variables. We will use linear regression for normally distributed outcomes and logistic regression for binary outcomes. Continuous variables with non-normal residuals will be log-transformed with effects reported as a % change.
  - Seated diastolic blood pressure
    - Continuous variable, normal distribution
  - Standing blood pressure
    - Continuous variable, normal distribution
  - Orthostatic hypotension
    - Binary variable, binomial distribution
  - Timed Up and Go Test
    - Continuous variable, normal distribution
  - Urinary sodium, potassium, and creatinine excretion
    - These may require log-transformation; anticipate continuous variables, normal distribution
  - Orthostatic symptoms
    - Binary variables (severe vs not), binomial distribution

**Handling of missing data:** We will employ a number of recommended strategies to prevent missing data:

- A simplified data collection schedule that minimizes participant burden;
- Intention-to-treat analysis that includes following participants according to the data collection schedule regardless of compliance with the study intervention;
- Frequent engagement with the participants through visit reminder calls or notes;
- A 24-hour phone number that participants can contact for questions and support;
- Contiguous windows of time during which specific follow-up visits are allowed;
- Monetary incentives to encourage enrollment and continued participation;
- Rigorous training of clinic staff emphasizing the importance of
  - Positive and warm interpersonal relationships between the participants and study staff
  - Study commitment during the consent process to ensure that potential participants understand the importance of completing the study
  - Addressing participant concerns to minimize dissatisfaction
  - Collecting data even if a participant discontinues the study treatment
  - Reasons for any drop-outs will be documented.

We will perform the following sensitivity analyses using established methods for addressing missingness in clinical trials: multiple imputations, best and worst-case scenarios, and use of the drop out event as a study end-point. We will compare the results from these approaches with primary analysis results to assess the primary result's robustness to the effects of missing data. Further, we will compare the baseline characteristics of complete cases and participants with missing measures between the two assignments.

### **Safety outcomes**

We will compare self-reported symptoms that are thought to potentially arise from the diets. The symptoms will be summarized by the counts and proportions of participants in each group and overall. The treatment groups will be compared with respect to safety outcomes by using a chi-square test (Fisher exact test when there are cell counts less than 5).

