### Baseline Assessments

For participants who have successfully been screened for eligibility and are enrolled into the study, baseline assessments will be performed against which to measure the study outcome. Run-In visit and baseline visit are described below.

- **Visit 2 [Randomization/baseline visit (RZ/BV1b)]:**
  - *Weight*
  - *Timed up and go test*
  - *Urine specimens*
  - *Symptoms and adverse events associated with sodium and orthostatic hypotension (headache, lightheadedness, dizziness, fatigue, etc.)*
- **Visit 3 [Run-In Visit, 1-2 days before meal delivery starts]:**
  - *Seated blood pressure*
  - *Weight*

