### 7.2 Methods and Timing of Assessing, Recording, and Analyzing Safety Parameters

Participants will be asked about any adverse food reactions and any fall history prior to feeding, 7-days into the study, and after the study is complete. We will also monitor blood pressure at day 10 of the study. We will use the following definitions of adverse events and serious adverse events.

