### 7.3 Adverse Events and Serious Adverse Events

**Adverse Event (AE):** any untoward or unfavorable medical occurrence in a participant, temporally associated with the participants' involvement in research (i.e., after RV), whether or not considered related to participation in the research, including:

- New disease diagnosis or illness
- Worsening of pre-existing disease or illness
- New or worsening symptom or sign

**Serious Adverse Event (SAE):** an adverse event that meets 1 or more of these criteria:

- Results in death
- Requires or prolongs hospitalization
- Is life threatening
- Results in persistent or significant disability or incapacity
- Results in congenital abnormality or birth defect
- Is a condition which the investigator judges to represent a significant hazard

- Is a SOTRUE-specific serious adverse event:
    - A fall event
    - An allergic reaction
    - Extremely high or low blood pressure measurements or high pulse rate\*
      - Systolic blood pressure >180 mm Hg
      - Systolic blood pressure < 90 mm Hg
      - Diastolic blood pressure >110 mm Hg
      - Diastolic blood pressure < 40 mm Hg
      - Pulse rate > 120 beats per minute
- \*Low blood pressures may require discontinuation of the study intervention.

In the current project, no laboratory values are collected to assess safety.

During the screening, run-in, intervention day 10-13, and follow up visits participants will have their blood pressure checked. An algorithm will be followed by the research assistant for persons with abnormal blood pressures to refer them to appropriate healthcare, and to notify the study physician(s). At the baseline, telephone, and follow up visits information will be collected from participants about any adverse events, which will be reported to the study physician(s).

Solicited adverse events include uncomfortable fullness, hunger, bloating, constipation, diarrhea, excessive thirst, fatigue, headache, lightheadedness with standing, nausea, falls, falls with injury, allergic reactions (including food related), and any hospitalizations. Additionally, the participant may contact the study physician by phone in the event of a fall or serious adverse event (hospitalization).

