### 7.3 Reporting Procedures

Pursuant to our ethical and regulatory responsibilities as well as to determine if further participation in the study is appropriate, we will provide participants contact information and request them to notify us of any new health issue or accident, particularly any falls. We will capture details of any adverse events occurring from the time of randomization to study completion or to document absence of adverse events during the study period.

If any AE or SAE is reported the research assistant will inform the study physician, who will determine if it is safe for the person to continue in the study.

Serious adverse events will be tracked until resolution or the end of the participant's involvement in the study. The principal investigator will report any SAE to the Hebrew SeniorLife IRB.

For extreme blood pressure measurements observed at any time during the study we will adhere to the following procedure:

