4.2 Secondary Endpoints

We will examine the effect of the low sodium diet on the following additional outcomes, testing the null hypothesis that there is no difference in the following outcomes between the low sodium diet and usual sodium diet intervention. We will examine the distribution of all variables. We will use linear regression for normally distributed outcomes and logistic regression for binary outcomes with and without adjustment for baseline. Continuous variables with non-normal residuals will be log-transformed with effects reported as a % change. If residuals are still not normally distributed even after log transformation we will apply non-parametric approaches.

- A. Seated diastolic blood pressure (average of two measurements days 12 and 14)
 - Continuous variable, normal distribution; as a sensitivity we will also examine last diastolic blood pressure measurement alone
- B. Standing blood pressure
 - Continuous variable, normal distribution

- C. Orthostatic hypotension
 - Binary variable, binomial distribution
- D. Timed Up and Go Test
 - Continuous variable, normal distribution
- E. Urinary sodium concentration, potassium concentration, sodium/creatinine ratio, potassium/creatinine ratio, and sodium/potassium ratio
 - These may require log-transformation; anticipate continuous variables, normal distribution
- F. Orthostatic symptoms
 - Binary variables (severe vs not), binomial distribution
- G. Side effects (5-point Likert scale)
 - Depending on the distribution of responses, side effect data will be analyzed as a continuous variable or dichotomized (none or any symptoms)

5 Missing data

We will employ a number of recommended strategies to prevent missing data:

- A simplified data collection schedule that minimizes participant burden;
- Intention-to-treat analysis that includes following participants according to the data collection schedule regardless of compliance with the study intervention;
- Frequent engagement with the participants through visit reminder calls or notes;
- A 24-hour phone number that participants can contact for questions and support;
- Contiguous windows of time during which specific follow-up visits are allowed;
- Monetary incentives to encourage enrollment and continued participation;
- Rigorous training of clinic staff emphasizing the importance of
 - Positive and warm interpersonal relationships between the participants and study staff

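### The dedicated safety test makes no use of the pre-diet symptom record, and neither document plans a by-arm summary of serious adverse events

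*Protocol*

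**What the plan says.** The safety paragraph of protocol 9.5 and SAP section 6 share their wording. The analysis is: "We will compare self-reported symptoms that are thought to potentially arise from the diets". The summary is: "The symptoms will be summarized by the counts and proportions of participants in each group and overall". The arms are compared by chi-square, or by Fisher's exact test when cells are small. Neither text gives a time point, a severity threshold, a rule for complaints already present, or a significance level.

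Elsewhere the protocol supplies what such a rule would need:

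- Sections 7.3 and 7.5 include in the definition of an adverse event a "New or worsening symptom or sign".
- The Visit 2 list in 6.2.2 includes "Symptoms and adverse events associated with sodium and orthostatic hypotension". Section 7.2 sets the questions on food reactions and falls at three times: "prior to feeding, 7-days into the study, and after the study is complete". The schedule in 6.1 has symptoms and adverse events at Visits 2, 4 and 6.
- The reporting sections (7.3 and 7.6) fix the window: "We will capture details of any adverse events occurring from the time of randomization to study completion".

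Sections 7.3 and 7.5 also list trial-specific serious adverse events: a fall, an allergic reaction, and five measured extremes (systolic pressure high or low, diastolic pressure high or low, fast pulse). These are tracked and reported to the IRB. Neither document plans to tabulate them by arm.

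SAP 4.2 lists orthostatic symptoms (item F, severe or not) and side effects on a 5-point scale (item G) as secondary endpoints, modelled both with and without a baseline term. For item G, "side effect data will be analyzed as a continuous variable or dichotomized (none or any symptoms", depending on the distribution.

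**The concern.** The adverse event definition and the safety test do not match. Residents aged 60 and over may arrive with fatigue, constipation, headache or light-headedness on standing, all of which are solicited. If a 2x2 table counts whoever reports a symptom, an unchanged long-standing complaint counts as much as one that began on the diet. The data that would separate them are collected but not used. Because the text is silent, the counting rule could also be chosen after the data are seen.

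On serious events, the synopsis motivates the trial by worry that low sodium may cause orthostatic hypotension and falls, and section 7.1 names blood pressure fluctuation and fall risk as the hazards. There is no formal DSMB (7.4) and no interim analysis (9.3), so the final tables are the only planned look at safety between arms. As written, they would not show how many participants in each arm crossed a blood pressure or pulse threshold that the protocol classes as serious.

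**Working it through.** **Numbers available.** Protocol 9.2 and SAP 3.2 give a difference of 9.53 mm Hg, SD 10.46, two-sided 0.05 and 80% power. The normal formula gives 2 × (1.960 + 0.842)² × (10.46/9.53)² = 18.9, so 19 per arm. The noncentral t gives 20 per arm (power 0.802). Then 40/0.90 = 44.4, so 45. The plan's 20 per arm and 45 recruited reproduce, and 20 per arm is used below.

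**Assumptions (the documents give no symptom rates).** Baseline prevalence p0 is 20 to 50%. Of those symptomatic at Visit 2, 80% still report the symptom later. Of those symptom-free, a share q reports it later: 5% on usual and 35% on low sodium. A share w of those symptomatic at Visit 2 gets worse, 10 to 30%, the same in both arms. Tests are two-sided at 0.05.

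**Formulas, per arm.**

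- Symptom reported, Visit 2 ignored: 0.8·p0 + (1 − p0)·q
- New onset only: (1 − p0)·q
- New or worsened: (1 − p0)·q + w·p0
- Variance of the arm difference: [pa(1 − pa) + pb(1 − pb)]/20

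The expected arm difference is (1 − p0) × 0.30 on all three, so only the variance changes.

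**Example, p0 = 40%.** Visit 2 ignored: 0.35 vs 0.53, variance (0.2275 + 0.2491)/20 = 0.0238. New onset: 0.03 vs 0.21, variance (0.0291 + 0.1659)/20 = 0.00975. New or worsened with w = 20%: 0.11 vs 0.29, variance (0.0979 + 0.2059)/20 = 0.0152. The ratios are 0.0238/0.00975 = 2.4 and 0.0238/0.0152 = 1.6.

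| p0 | SE, Visit 2 ignored | SE, new onset | Variance ratio vs new onset | Variance ratio vs new or worsened, w = 10 / 20 / 30% |
|---|---|---|---|---|
| 20% | 0.143 | 0.110 | 1.7 | 1.5 / 1.4 / 1.3 |
| 30% | 0.150 | 0.105 | 2.0–2.1 | 1.7 / 1.5 / 1.4 |
| 40% | 0.154 | 0.099 | 2.4 | 1.9 / 1.6 / 1.4 |
| 50% | 0.156 | 0.092 | 2.9 | 2.0 / 1.6 / 1.3 |

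The last column is the relevant one, because the protocol's definition covers worsening as well as onset.

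**Power and size.** Binomial probabilities were summed over all tables with Fisher p ≤ 0.05. For p0 = 20/30/40/50%, power with Visit 2 ignored is 27/19/12/8%, and for new onset 44/35/26/17%. With onset 5% in both arms and Visit 2 ignored, the test rejects about 2.3 to 2.5% of the time, below its nominal 5%.

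**Serious events at 20 per arm.** Fisher's test gives p = 0.106 for 0 vs 4 and p = 0.047 for 0 vs 5. Its power is 3% for assumed rates of 2% vs 10%, and 27% for 2% vs 20%. With no events in an arm, the exact 95% upper limit is 1 − 0.025^(1/20) = 17%. Such a table can describe, but can hardly test.

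**The case against.** Several stronger readings are tempting, and the documents do not support them.

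- **That the safety test counts any symptom.** The safety paragraph never says so. It refers to symptoms thought to come from the diets and is silent on timing and baseline. The none-or-any split appears only in SAP 4.2 G, as one of two options. The fair criticism is that the rule is missing.
- **That pre-existing complaints hide diet effects throughout the plan.** SAP 4.2 models orthostatic symptoms and side effects with a baseline term as well as without. On item F, a move from mild to severe changes category, and an unchanged mild symptom does not. The problem is confined to the dedicated safety test and the unadjusted models. It remains there, because the adjusted models are secondary-endpoint analyses and are not named as the safety result. Protocol 9.5 does not list side effects as a secondary endpoint at all.
- **That chance imbalance in baseline symptoms could produce a false safety signal.** Randomization puts that imbalance inside the test's error rate, and the size computed above is under 5%. The loss is of precision.
- **That every trial-specific serious event is left out.** Falls, allergic reactions and hospitalizations are solicited from participants and might be counted as self-reports. Only the five measured thresholds clearly cannot be.
- **That blood pressure harm is never compared.** Seated and standing pressure and orthostatic hypotension are compared by arm. Those analyses still do not show who crossed a threshold.

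It is also fair to say that entry requires a systolic pressure of 100 to 149 mm Hg, that study physicians review events, and that a comparison of rare events in 40 to 45 people will be mainly descriptive. That argues for a table without a test. It does not argue for having no table.

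**Conclusion.** The point holds in a limited form. The dedicated safety test sets aside the protocol's own new-or-worsening definition and the pre-diet record. The cost is lost precision in that test, of the order of a 1.3- to 2.0-fold variance under the assumed prevalence, persistence, onset and worsening rates. The higher ratios of 1.7 to 2.9 apply only to an endpoint restricted to new onset. If worsening itself differed by arm, a test that ignores Visit 2 would miss that part as well. The missing by-arm summary of serious adverse events rests on no assumed rates: no such summary is planned, and the measured events have no route into a self-report comparison. The primary analysis is not affected. Both gaps are worth closing because the data are already collected. One assumption is that the same symptoms are rated on the same scale at Visits 2, 4 and 6, which the documents imply but do not spell out.

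**What to change.** 1. In protocol 9.5 and SAP 6, define the safety event for each symptom as new or worse at Visit 4 or Visit 6 than in the same participant's Visit 2 record. Compare the proportions by Fisher's exact test and print the Visit 2 prevalence by arm beside them.
2. Keep the baseline-adjusted side-effect model of SAP 4.2 G alongside this, and say in SAP 6 that it supports the safety result. It retains rating detail that a worse-or-not split discards.
3. Confirm in the SAP that the symptom items and scale are the same at the three visits.
4. Add a descriptive table by arm, with exact intervals, of participants with each of the seven trial-specific serious adverse events and any other serious event. Count from randomization, as the reporting sections do, and flag events before the first study meal, since randomization precedes the diet.

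The cost is wording in two documents and one extra table, with no new data collection if step 3 is confirmed. Participants already at the top rating at Visit 2 cannot worsen, which is a further reason to show the Visit 2 distribution.
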